11.3.2 Safety population

The primary analysis population is the safety population, which is defined as all patients who have actually received at least one dose or part of a dose of dupilumab in the LTS12551 study.

The treatment-emergent period is defined as the time from the first dose of dupilumab in LTS12551 up to the last dose of dupilumab plus 2 weeks (corresponding to one dose interval) plus 12 weeks (follow-up period duration). The pre-treatment period is defined as the time from the starting of AE reporting in LTS12551 study up to the first dose of dupilumab in LTS12551.

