11.4.3.1.2 Adverse Events of Special Interest

The following summaries will be generated:

- Incidence of each AESI will be tabulated.
- The time-to-first event analyzed using Kaplan-Meier methods and displayed as Kaplan-Meier plots (cumulative incidence [%] versus time based on Kaplan-Meier estimates) will be provided to depict the course of onset over time. Number of treatment-emergent AESIs per 100 patient-years (total number of events adjusted for the total duration of exposure) will be presented by decreasing incidence of PT.
- An overview summary of the number (%) of patients with:
 - Any TEAE.
 - Any serious AE (regardless of treatment-emergent status).

- Any treatment-emergent SAE.
- Any AE leading to death.
- Any TEAE leading to permanent study drug discontinuation.
- Any TEAE by maximum intensity, corrective treatment, and final outcome.
- Cumulative incidence (Kaplan-Meier estimates) up to specified time points.

AESI definitions and the method to identify AESIs will be specified in the SAP.

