Patients from EFC13579, EFC13691 or PDY14192 who complete the entire planned treatment period may be eligible for enrolling into LTS12551 immediately at the end of treatment (EOT) visit of the parent study. In other words, for patients coming from these 3 studies, the end of treatment visit of parent study should be combined with Visit 1 and Visit 2 of LTS12551, so there is no gap in dosing, and screening and loading dose at Day 1 are not applicable.

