1.6 STATISTICAL MODIFICATIONS MADE IN THE STATISTICAL ANALYSIS PLAN

This statistical analysis plan (SAP) version 3.0 is based on the LTS12551 amended protocol 2 (protocol amendment 4) dated October 31st, 2016, and is the third version of SAP for LTS12551.

SAP version number	Date approved	Rationale	Description of statistical changes
2	23-Nov-2016	Protocol amendment 4 shortens the open-label treatment period to 48 weeks.	The open-label treatment duration is amended to 48 weeks for patients providing consents after the implementation of the protocol amendment 4.
2	23-Nov-2016	Protocol amendment 4 drops the electronic diary, PEF meter, EQ-5D-3L, serum immunoglobulins, and serum total IgE for all the patients in LTS12551 study. Before the protocol amendment 4 becomes effective, the patients from	The analyses for AM/PM PEF, AM/PM asthma symptom score, number of reliever uses, number of nocturnal awakenings, EQ-5D-3L score, serum immunoglobulins and serum total IgE in LTS12551 study will be restricted to the patients from the DRI12544 study and performed to the data observed up

SAP			
version	Date		
number	approved	Rationale	Description of statistical changes
		DRI12544 study have data collection for the aforementioned endpoints for more than one year, while only a few of patients from EFC13579, EFC13691 or PDY14192 studies have limited amount of data collected for those endpoints.	to the end of their collection. The compliance for background controller medications will be calculated using the data observed up to the end of the electronic diary collection.
2	23-Nov-2016	Protocol amendment 4 adds three efficacy endpoints linked to the prescribed OCS dose for the patients from the EFC13691 study only. They are the percentage change from baseline in the OCS dose, the proportion of patients achieving a reduction of 50% or greater in the OCS dose compared with the baseline, and the proportion of patients whose background OCS are completely tapered off. The baseline OCS dose is defined as the original baseline value of the parent study.	The proportion of patients whose background OCS are completely tapered off and its analysis have been added to this version of SAP, and the other two endpoints linked to the OCS dose and their corresponding analyses have already existed in the SAP 1.0.

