2.3.2 Safety population

The safety population is defined as the patients who have actually received at least 1 dose or part of a dose of the IMP in LTS12551.

Enrolled patients for whom it is unclear whether they took the IMP or not will be included in the safety population as enrolled.

The treatment category "Placebo/Dupilumab" is defined as the patients who have been in the actual placebo arms of the parent studies and exposed to Dupilumab in LTS12551. The treatment category "Dupilumab/Dupilumab" is defined as the patients who have been in the actual Dupilumab arms of the parent studies and exposed to Dupilumab in LTS12551.

For the OCS dependent patients, results of each planned analysis will be presented by "Placebo/Dupilumab", "Dupilumab/Dupilumab" and "All".

For the non-OCS dependent patients, results of each planned analysis will be presented by the parent study and "All", and further by "Placebo/Dupilumab" and "Dupilumab/Dupilumab" within each parent study.

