2.4.3.1 Extent of investigational medicinal product exposure

The extent of IMP exposure will be assessed by the duration of IMP exposure in LTS12551 study.

Duration of investigational product exposure is defined as: the last IMP dose date in LTS12551 study – the first IMP dose date in LTS12551 study + 14 days, regardless of unplanned intermittent discontinuations (see Section 2.5.3 for calculation in case of missing or incomplete data).

Duration of IMP exposure will be summarized descriptively as a quantitative variable (number, mean, SD, median, minimum, and maximum). In addition, duration of treatment exposure will also be summarized categorically by counts and percentages for each of the following categories and cumulatively according to these categories (the categories exceeding Week 48 may apply to only the patients on the 96-week treatment period who signed the informed consent form before the approval of protocol amendment 4):

 \leq 4 week

- > 4 and \leq 12 weeks
- > 12 and ≤ 24 weeks
- > 24 and ≤ 48 weeks
- > 48 and \leq 72 weeks
- > 72 and \leq 96 weeks
- >96 weeks

Additionally, the cumulative duration of treatment exposure, will be provided in patient years by treatment category and overall (see Section 2.3.2).

Number and percentage of patients will be summarized by total number of injections they received during the LTS12551 study. The number and percentage of patients who receive injection will be summarized by type of administrator (site staff, patient or non-professional care giver, professional care giver at home), by dosing week, and maybe by IMP packaging way (vial or pre-filled syringe).

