- All treatment-emergent serious adverse events by primary SOC and PT, showing number (%) of patients (including total patient years in column headers) with at least one TEAE, will be presented by SOC internationally agreed order and decreasing incidence of PTs within SOC.

Analysis of all treatment-emergent adverse event(s) leading to treatment discontinuation

- All TEAEs leading to treatment discontinuation, by primary SOC, HLGT, HLT, and PT, showing the number (%) of patients (including total patient years in column headers) will be presented by the internationally agreed SOC order. The other levels (HLGT, HLT, PT) will be presented in alphabetical order.
- All TEAEs leading to treatment discontinuation, by primary SOC and PT, showing number (%) of patients (including total patient years in column headers) with at least one TEAE, will be presented by SOC internationally agreed order and by decreasing incidence of PTs within each SOC.

Analysis of adverse events of special interest (AESI) and other selected AE groupings

Summaries of AESI defined by the search criteria:

- All treatment emergent AESIs and other selected AE groupings identifiable by MedDRA terms or by laboratory values (as in ALT elevation), by AESI category and PT, showing the number (%) of patients (including total patient years in column headers), will be presented by decreasing incidence of PT within each AESI category.
- An overview summary within each treatment-emergent AESI and other selected AE groupings will include:
 - Number (%) of patients with any TEAE
 - Number (%) of patients with any SAE (regardless of treatment-emergent status)
 - Number (%) of patients with any treatment-emergent SAE
 - Number (%) of patients with any AE leading to death

- Number (%) of patients with any TEAE leading to permanent treatment discontinuation
- Number (%) of patients with any TEAE by maximum intensity, corrective treatment, and final outcome
- Number (%) of patients with any possibly related TEAE
- Kaplan-Meier plot (cumulative incidence (%) versus time up to Week 60 based on K-M estimate) for time-to-onset of the first TEAE
- Cumulative incidence (K-M estimates) up to specified time points (Week 4, Week 12, Week 24, Week 48, Week 60)

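### AESI Kaplan-Meier outputs stop at Week 60, although the 2-year cohort, including every DRI12544 patient, is treated to Week 96 and at risk to Week 108

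*SAP*

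**What the plan says.** SAP 2.4.5.1 lists, within the overview for each AESI and other selected AE grouping, a "Kaplan-Meier plot (cumulative incidence (%) versus time up to Week 60 based on K-M estimate) for time-to-onset of the first TEAE". The next item is "Cumulative incidence (K-M estimates) up to specified time points (Week 4, Week 12, Week 24, Week 48, Week 60", and no later time point is given.

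Protocol 11.4.3.1.2 describes the same time-to-first-event analysis, "displayed as Kaplan-Meier plots (cumulative incidence [%] versus time based on Kaplan-Meier estimates) will be provided to depict the course of onset over time". It sets no horizon for the plot and leaves the tabulated time points to be specified.

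The treatment-emergent period (Protocol 11.3.2, matched by SAP 2.1.4) runs from the first LTS12551 dose "up to the last dose of dupilumab plus 2 weeks (corresponding to one dose interval) plus 12 weeks (follow-up period duration". Protocol 6.1 and 6.2.1 keep patients enrolled before Amendment 04 on 96 weeks of treatment and put later enrollees on 48. Protocol 6.2.1 also records that DRI12544 enrollment was already complete.

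Other SAP outputs go further. The exposure categories in SAP 2.4.3.1 extend beyond 96 weeks, with the remark that "the categories exceeding Week 48 may apply to only the patients on the 96-week treatment period". The safety visit windows in SAP 2.5.4 reach the Week 108 end-of-study visit.

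**The concern.** The limit equals the end of follow-up of the shorter cohort and is applied to everyone. Kaplan-Meier estimation deals with unequal follow-up by censoring, so the presence of 1-year patients does not by itself require the curve to stop where they leave. Nor does a common horizon explain it for DRI12544. SAP 2.3.2 states "For the non-OCS dependent patients, results of each planned analysis will be presented by the parent study", and the DRI12544 column contains only 2-year patients.

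Protocol 4.2 says the study should help to identify late-onset adverse events. An AESI that starts after Week 60 is counted in the n (%) tables and the rates per 100 patient-years (SAP 2.4.5.1) and appears in the listings (Protocol 11.4.3.1.3). A single percentage or rate cannot show whether the hazard rises, falls or stays level after the first year, and a listing has no risk set. The time-to-onset curve is the planned output that could answer that question.

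The later data were foreseeable. The version 2 entry in SAP 1.6 (23-Nov-2016) notes that patients from the "DRI12544 study have data collection for the aforementioned endpoints for more than one year". SAP version 3 is dated 20-Jul-2017, about 34 weeks later, so such patients still in the study were at roughly Week 86 (52 + 34) or beyond when the limit was kept. SAP section 3 applies every planned analysis to the interim report for the asthma submission, so the limit applies there too.

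**Working it through.** **Where each cohort's risk period ends.** The end-of-treatment visit is 2 weeks after the last dose (Protocol 10.1.1.16 and 10.1.2.12). The treatment-emergent period ends at last dose + 2 + 12 weeks.

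| Cohort | Treatment | Last dose | End of risk |
|---|---|---|---|
| Enrolled before Amendment 04 | 96 weeks | 96 − 2 = Week 94 | 94 + 2 + 12 = Week 108 |
| Enrolled after Amendment 04 | 48 weeks | 48 − 2 = Week 46 | 46 + 2 + 12 = Week 60 |

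These match the synopsis maximum durations of 108 and 60 weeks (96 + 12 and 48 + 12; 111 with 3 weeks of DRI12544 screening).

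**Time outside the Kaplan-Meier window, per 2-year patient.**

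- Completer, at-risk time: 108 − 60 = 48; 48/108 = 44.4%.
- Completer, treatment time: 96 − 60 = 36; 36/96 = 37.5%.
- Last dose at Week 72: risk ends at 72 + 14 = Week 86; (86 − 60)/86 = 30.2%.
- Last dose at or before Week 46: nothing is lost.

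**Which exposure is not covered.** DRI12544 placebo/dupilumab patients start dupilumab in LTS12551, so onset is shown for 60 of their 96 dupilumab weeks. EFC13579 dupilumab/dupilumab patients bring 52 weeks of treatment and roll over on the same day, "so there is no gap in dosing" (SAP 1.1). By LTS12551 Week 48 they have 52 + 48 = 100 treatment weeks, so some long-exposure onset does fall inside the window. For any of them enrolled before Amendment 04, treatment continues to 52 + 96 = 148 weeks while the window closes at 52 + 60 = 112. Exposure weeks 113 to 148 (36 weeks) appear in no Kaplan-Meier output.

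**Illustration of the share of first events affected.** No AESI rate is given, so I assume a constant hazard and a Week-60 cumulative incidence p between 1% and 20%.

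- Full follow-up: F108 = 1 − (1 − p)^(108/60); share after Week 60 = (F108 − p)/F108.
- 30% lost at a constant rate by Week 108: k = −ln(1 − p)/60 − ln(0.7)/108; share = (e^(−60k) − e^(−108k))/(1 − e^(−108k)).

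| p | Full follow-up | 30% lost |
|---|---|---|
| 1% | 44.2% | 39.9% |
| 5% | 43.3% | 39.0% |
| 10% | 42.1% | 37.8% |
| 20% | 39.5% | 35.3% |

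**Whether enough patients would remain.** SAP 1.1 gives 776 patients enrolled in DRI12544; the number who rolled over is not stated. Assuming 50% to 90% rolled over and 70% to 90% of those are still followed at Week 60, the number at risk is 776 × 0.5 × 0.7 = 272 to 776 × 0.9 × 0.9 = 629.

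**Stated reasons.** SAP 1.5 and 1.6 list the statistical changes. None mentions Week 60 or the Kaplan-Meier outputs.

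**The case against.** The strongest reply is that nothing is contradicted and little is lost. The protocol leaves the tabulated time points open and sets no horizon for the plot, so the SAP has filled in a reporting choice. SAP 1.5 also records the view that one year of open-label data should suffice for the asthma program, and 48 + 12 = 60. The late events are not dropped: onset dates are collected, listings are planned, and the events enter the percentages and rates. The primary endpoint is untouched, and the safety analysis is descriptive throughout.

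Much of this is right, and it limits the point to one of analysis choice. It does not justify the limit. The protocol wants the plots to show how onset develops over time, and a plot cut at 60 of 108 weeks does so only in part for this cohort. The SAP 1.5 rationale explains the shorter treatment of later enrollees; it does not mention Kaplan-Meier and does not bear on patients kept on 96 weeks.

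Four further points have weight:

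- SAP 1.6 says only a few patients from the other parent studies had diary and similar data before Amendment 04. The group behind exposure weeks 113 to 148 may therefore be small, and the planned time axis is LTS12551 time rather than cumulative exposure.
- The event shares above largely restate 48/108, because they come from a constant hazard.
- Between Weeks 48 and 60, pooled curves combine 1-year patients in follow-up with 2-year patients on treatment. Because the treatment-emergent period includes follow-up, early discontinuers create such mixing at every week. This calls for labelling and is not a fault of the horizon.
- A pre-Amendment 04 curve is a new display population across 17 groupings (10 AESI, 7 other), many probably sparse.

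**Conclusion.** The concern holds. The AESI time-to-onset outputs end where the 1-year cohort leaves the risk set, and the SAP does not say why. For a 2-year completer this removes 44% of at-risk time and 37.5% of treatment time from the only planned output that estimates when AESIs begin; earlier discontinuers lose less. It is clearest for DRI12544, whose column has no 1-year patients.

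The loss is confined to onset timing. Counts, rates, listings and the primary endpoint are unaffected, and EFC13579 rollover patients supply some long-exposure information before Week 60. The week counts follow from the documents' own periods. The event shares of 35% to 44% rest on an assumed constant hazard, assumed incidence and assumed loss to follow-up. This should be corrected, given the study's late-onset aim and the small cost.

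**What to change.** In SAP 2.4.5.1, for DRI12544 and for all patients enrolled before Amendment 04, extend the Kaplan-Meier plots to Week 108 and add cumulative-incidence estimates at Weeks 72, 96 and 108, with numbers at risk. On any pooled curve, mark Week 48, when the 1-year cohort ends treatment, and Week 60, when it leaves the risk set. If a common horizon is wanted for the pooled population, keep the Week 60 summary there and state that reason.

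The data are already collected. The cost is SAP wording, a longer axis and three time points for the DRI12544 column, plus an added set of displays for the pre-Amendment 04 cohort, which the by-parent-study layout does not currently provide.

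Estimates after Week 60 describe only the pre-Amendment 04 cohort and are less precise. As a rough guide with an assumed 200 to 400 patients at risk, a 5% estimate has a 95% half-width of 1.96 × √(0.05 × 0.95/n), which is 3.0 percentage points at n = 200 and 2.1 at n = 400. Numbers at risk under the plot would make that visible.

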2.4.5.2 Deaths

The following death summaries will be generated on the safety population, unless otherwise specified.

- Number (%) of patients (including total patient years in column headers) who died by primary SOC and PT for death
- Deaths in non-enrolled patients or enrolled but not treated patients
- TEAE leading to death (death as an outcome on the AE CRF page as reported by the Investigator) by primary SOC and PT showing number (%) of patients (including total patient years in column headers) sorted by internationally agreed SOC order, and by alphabetical order of PT within each SOC.
- All pre-treatment AE leading to death by primary SOC and PT, showing the number (%) of patients (including total patient years in column headers), sorted by the internationally agreed SOC order and by decreasing incidence of PTs within each SOC.
- Listing of deaths showing parent study, treatment category, patient identifier, gender, race, age, duration of exposure, date of death (if relevant), reason of death.

2.4.5.3 Analyses of laboratory variables

The baseline value of all laboratory variables is the original baseline from the parent studies. The pre-dose measurement at Week 0 of LTS12551 will be separately presented in the summaries or plots over time. This section will be organized by biological function as in Section 2.1.4.3.

The summary statistics (including number, mean, median, standard deviation, Q1, Q3, minimum and maximum) of all laboratory variables (central laboratory values and changes from baseline) will be calculated for each visit or study assessment (baseline, each post-baseline time point, and endpoint) by the treatment category and overall (see Section 2.3.2).

For all laboratory variables, the mean change from baseline with corresponding standard error at each visit will be plotted by the treatment category and overall (see Section 2.3.2).

For all laboratory variables, the summary statistics over visits for either measurements or mean change from baseline, and the plot of mean change from baseline over visits should use the centralized data only, and should include the measurements obtained at either scheduled or unscheduled visits.

The incidence of PCSAs (list provided in Appendix A) at any time during the treatment-emergent adverse event period will be summarized by biological function, and by the treatment category and overall (see Section 2.3.2), regardless of the baseline level and/or according to the following status at baseline of parent study and at Week 0 of LTS12551 study, respectively:

• Normal/missing

• Abnormal according to PCSA criterion or criteria

For parameters for which no PCSA criterion is defined, similar table(s) using the normal range will be provided.

For PCSA analyses, the laboratory measurements obtained at either scheduled or unscheduled visits should be used; and, both the centralized and local test results should be used, as long as their available dates/time is different from each other's. Centralized data will be used preferentially to the local measures in the PCSA analyses when measurements are performed on the same date and at the same time for a given laboratory test.

A listing of patients with at least one post-baseline PCSA will be provided and will display the whole profile over time of all parameters of the corresponding biological function. In this listing, baseline, endpoint value and individual values will be flagged when lower or higher than the lower or upper laboratory limits and/or when reaching the absolute limit of abnormality criteria.

Drug-induced liver injury

Additional analysis of liver-related adverse events will be performed if necessary.

2.4.5.4 Analyses of vital sign variables

The baseline value of all vital sign variables is the original baseline from the parent studies. The pre-dose measurement at Week 0 of LTS12551 will be separately presented in the summaries or plots over time.

The summary statistics (including number, mean, median, standard deviation, Q1, Q3, minimum and maximum) of all vital signs variables (measurements and changes from baseline) will be calculated for each visit or study assessment (baseline, each post-baseline time point, and endpoint) by the treatment category and overall (see Section 2.3.2).

For all vital sign variables, the mean change from baseline with corresponding standard error at each visit will be plotted by the treatment category and overall (see Section 2.3.2).

For all vital sign variables, the summary statistics over visits for either measurements or mean change from baseline, and the plot of mean change from baseline over visits should include the measurements obtained at either scheduled or unscheduled visits.

The incidence of PCSAs at any time during the treatment-emergent adverse event period will be summarized by the treatment category and overall (see Section 2.3.2), irrespective of the baseline level and/or according to the following status at baseline of parent study and at Week 0 of LTS12551 study, respectively:

- Normal/missing
- Abnormal according to PCSA criterion or criteria

For PCSA analyses, the vital sign measurements obtained at either scheduled or unscheduled visits should be used.

2.4.5.5 Analyses of electrocardiogram variables

The baseline value of all ECG variables is the original baseline from the parent studies. The predose measurement at Week 0 of LTS12551 will be separately presented in the summaries or plots over time.

The summary statistics (including number, mean, median, standard deviation, Q1, Q3, minimum and maximum) of all ECG variables (measurements and changes from baseline) will be calculated for each visit or study assessment (baseline and each post-baseline time point, and endpoint) by the treatment category and overall (see Section 2.3.2).

For all ECG parameters, the mean change from baseline with corresponding standard error at each visit will be plotted by the treatment category and overall (see Section 2.3.2).

For all ECG variables, the summary statistics over visits for either measurements or mean change from baseline, and the plot of mean change from baseline over visits should use the centralized data only, and should include the measurements obtained at either scheduled or unscheduled visits.

The incidence of PCSAs at any time during the treatment-emergent adverse event period will be summarized by treatment category and overall (see Section 2.3.2) irrespective of the baseline level and/or according to the following status at baseline of parent study and at Week 0 of LTS12551 study, respectively:

- Normal/missing
- Abnormal according to PCSA criterion or criteria

For PCSA analyses, the ECG measurements obtained at either scheduled or unscheduled visits should be used; and, both the centralized and local ECG results should be used, as long as their available dates/time is different from each other's. Centralized data will be used preferentially to the local measures in the PCSA analyses when measurements are performed on the same date and at the same time.

